Questionnaires. The subjects' impressions of the effectiveness of the intervention, the dose, and the ease of using the device/equipment will be captured with questionnaires including the Stroke Impact Scale Hand Section, the Neuro-QOL Upper Extremity Function Fine Motor ADL from the Patient Reported Outcomes Measurement Information System (PROMIS) Neuro-QOL Bank, and an end-of-treatment questionnaire. The purpose is to gain insight into how well the device and dosage are tolerated and the subjects' perception of effectiveness. The questionnaires will be administered at end of treatment by a staff member who will have no other interaction with the subjects.

Other Measures. Additional secondary measures include changes in muscle tone (modified Ashworth scale) and finger flexion and extension strength (dynamometry). These outcomes along with the

baseline characteristics collected and treatment adherence may provide insight into mechanisms of action and interpretation of the main findings.

Experimental Flow

Participation time for each subject will be ~9.5 months (inc. 3 months treatment, 6months follow-up).

There are a total of 29 visits involved in this study.

Visit 1. Consent and eligibility (2 hrs)

Visit 2. Baseline Assessment (2 hrs)

Visit 3. Randomization, Device Setup and Training (2 hrs)

Visits 4-14. Therapy Visits (1.5 hrs)

Visit 15. Mid-Treatment Outcome Assessment (2 hrs)

Visits 16-26. Therapy Visits (1.5 hrs)

Visit 27. End of Treatment Outcome Assessment (2 hrs)

Visit 28. 3-mo post-Treatment Outcome Assessment (2 hrs)

Visit 29. 6-mo post-Treatment Outcome Assessment (2 hrs)

Selection Criteria

Inclusion Criteria

- Age 21 to 90 years old at time of randomization
- 6 to 24 months since a first clinical cortical or subcortical, ischemic or hemorrhagic stroke
- unilateral upper limb hemiparesis with finger extensor strength of \leq grade 4/5 on the Medical Research Council (MRC) scale
- score of $\geq 1/14$ and $\leq 11/14$ on the hand section of the upper extremity Fugl-Meyer Assessment
- adequate active movement of shoulder and elbow to position the paretic hand in the workspace for table-top task practice
- able to follow 3-stage commands
- able to recall at least 2 of a list of 3 items after 30 minutes
- skin intact on hemiparetic arm

- surface electrical stimulation of the paretic finger and thumb extensors produces functional hand opening without pain (this will exclude patients who have too much flexor spasticity)

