- able to hear and respond to cues from stimulator
- not receiving occupational therapy (no concomitant OT)
- full volitional hand opening/closing of contralateral hand
- demonstrates ability to follow instructions for putting on and operating the assigned stimulator or has caregiver to assist

Exclusion Criteria

- co-existing neurologic diagnosis of peripheral nerve injury, Parkinson's disease, spinal cord injury, traumatic brain injury, or multiple sclerosis
- uncontrolled seizure disorder, defined as having a seizure within the previous 3months
- brainstem stroke
- uncompensated hemi-neglect (extinguishing to double simultaneous stimulation)
- severe shoulder or hand pain, i.e., unable to position hand in the workspace without pain
- insensate to touch on forearm or hand
- history of potentially fatal cardiac arrhythmias with hemodynamic instability
- cardiac pacemaker or other implanted electronic system
- botulinum toxin injections to any upper extremity muscle within 3 months of enrolling
- pregnancy (unknown risks of surface NMES during pregnancy)
- lack of functional passive range of motion of the wrist or fingers of affected side
- diagnosis (apart from stroke) that substantially affects paretic arm and hand function
- deficits in communication that interfere with reasonable study participation
- lacking sufficient visual acuity to see the stimulator's display
- concurrent enrollment in another investigational study.

Potential Risks

Neuromuscular Electrical Stimulation Risks (pertain to CCFES and cNMES groups)

* Skin Irritation – When surface electrodes are used, it is possible that the subject will experience a temporary redness of the skin from either the electrodes, the conductive gel used with them, or any adhesive used to secure them. This risk is common. Skin irritation and redness from the electrical stimulation is also possible, but this possibility is rare and minimized by the type and intensity of stimulation that will be used. Participants will be instructed that redness should fade within an hour and that if redness persists, they should contact study staff. If necessary, electrodes or adhesives will be replaced with an alternative.

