* Uncomfortable Sensation – Electrical stimulation of a muscle may be perceived as a twitching or vibrating sensation and may be uncomfortable. Electrical stimulation of a nerve may be perceived as a strong but short shock and may be uncomfortable. Electrical stimulation of the skin may be perceived as a “pins and needles” sensation and may be uncomfortable. Discomfort is common but stimulus parameters will be adjusted to the subject’s comfort.

* Electrical Hazards – There is a possibility of an electrical shock hazard whenever electrical stimulation is used or whenever electrical equipment is used to make measurements. There is a possibility of an electrical burn whenever electrical stimulation with surface electrodes is used. The equipment to be used has been designed and tested to minimize these risks. Subjects will be trained how to use the stimulator safely and will be asked to adhere to a list of safety precautions. With these precautions, electrical hazards are rare.

* Stimulator Malfunction – There is a rare possibility that the stimulator may malfunction and produce painful stimulation after it has been programmed in the laboratory. The subject could feel a sudden burning sensation, which can damage the skin if it does not stop. The equipment to be used has been designed and tested to minimize this risk. If the subject experiences pain from the stimulation, they will be told to turn off the stimulator and/or unplug the electrode cables, stop using it, and contact study personnel.

* Unknown Effect of Stimulation on Pregnancy – The effect of electrical stimulation on a fetus is not known. If the subject is pregnant or is planning to become pregnant they may not participate in this

study. Subjects will be told to notify study personnel if they suspect that they become pregnant during the study.

All Groups

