In addition to the risk management for the study described above, subjects in the CCFES and cNMES groups will be given a group-specific user's manual that describes how to use the stimulator safely. This will be reviewed with each subject before they are sent home with the stimulator. The manual will list the following safety precautions:

Safety Information

- **IMPORTANT:** Avoid handling the electrodes while the stimulator is on! Always remember to turn off the stimulator before you remove the electrodes.
- Always wash and dry the skin before applying the electrodes. Any mild soap is fine; avoid deodorant or perfumed soaps or lotions, as these affect skin adherence.
- Use new electrodes if the reused ones no longer stick well to the skin.
- Place electrodes on the skin only where instructed.
- Never position electrodes on the chest, across the heart, or on the neck.
- Do not place electrodes over broken skin as this may cause pain and skin irritation.
- Do not submerge the stimulator in water, or use around water (spills, bathtub/shower or sink).
- Do not operate dangerous machinery or drive while using the stimulator.
- Do not sleep while using the stimulator. Remain attentive during use to avoid skin burns.
- A slight reddening of the skin under the electrode is normal. This should fade after 1 hour once the electrodes are removed. If you note redness or blistering beyond this, discontinue use and inform your therapist.
- The safety of electrical stimulation in pregnancy has not been determined; therefore, do not use the device if pregnant.
- Electrical stimulation should not be used by patients with implanted electronic devices (cardiac demand pacemakers etc.) unless under specialized medical supervision.
- Do not use the device if you have a history of potentially fatal cardiac arrhythmias.

- Electrical stimulation should not be used by people who have poorly controlled epilepsy.
- The stimulator has been programmed specifically for the intended user only. Do not allow anyone else to use the stimulator.

Statistical Analysis Plan

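### Read literally, the arrhythmia exclusion is narrower than the device manual's precaution, so a candidate could be randomised to a stimulator that the manual tells them not to use.

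*Combined protocol and SAP*

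**What the plan says.** The protocol states the arrhythmia rule in two places.

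- **Selection Criteria, Exclusion Criteria:** a candidate is excluded for a "history of potentially fatal cardiac arrhythmias with hemodynamic instability". A separate line excludes anyone with a pacemaker or another implanted electronic system.
- **Risk Management, Safety Information:** participants in the CCFES and cNMES groups receive a user's manual specific to their group. "The manual will list the following safety precautions", and one of them reads "Do not use the device if you have a history of potentially fatal cardiac arrhythmias". On timing, the section says "This will be reviewed with each subject before they are sent home with the stimulator".

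Two other places bear on the sequence. The Inclusion Criteria require that "surface electrical stimulation of the paretic finger and thumb extensors produces functional hand opening without pain", and this applies to every candidate whatever group follows. Experimental Flow puts consent and eligibility at Visit 1, and randomisation with device setup and training at Visit 3. On the standing of the precautions, the Electrical Hazards item under Potential Risks says "Subjects will be trained how to use the stimulator safely and will be asked to adhere to a list of safety precautions".

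**The concern.** The exclusion appears to need two things, a history of potentially fatal arrhythmia and haemodynamic instability. The manual needs only the first. If both texts mean what they literally say, eligibility admits a person whom the manual bars from using the device.

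Staff following both texts would enrol that person, randomise them and, in two of the three groups, set up a stimulator. They would then review a document with the participant that says not to use it. The participant could not follow both the precaution and the assigned home regimen of 10 sessions a week. A contraindication belongs at screening, before allocation, and should not first appear in take-home instructions. With four sites, the two wordings could also be applied differently from one site to another.

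**Working it through.** No sample size, power or error-rate figure is involved. The check is a comparison of texts.

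**Step 1: the two rules.** Let A be a history of potentially fatal arrhythmia and B be haemodynamic instability.

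| Source | Literal rule |
|---|---|
| Exclusion Criteria | Exclude if A and B |
| Manual, Safety Information | No device use if A |

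The difference is A without B.

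**Step 2: does another criterion close the gap?** The implanted-device exclusion removes anyone in the gap who has a pacemaker or similar system. No other inclusion or exclusion criterion concerns cardiac history. What remains is A, without B and without an implanted device.

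**Step 3: the path of such a person.** They pass the exclusion criteria, undergo the stimulation test needed for eligibility, and are randomised at Visit 3. If assigned to CCFES or cNMES, they receive the manual. It is specific to the group, so it comes after allocation. If assigned to TOT, they receive neither stimulator nor manual.

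**Step 4: do the other medical items match between the two texts?**

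| Item | Exclusion Criteria | Manual | Stricter text |
|---|---|---|---|
| Pregnancy | Barred | Barred | Same |
| Implanted device | Barred outright | Barred, with an exception under specialist supervision | Exclusion Criteria |
| Seizures | Uncontrolled, defined by a seizure in the past 3 months | Poorly controlled epilepsy, no time window | Similar idea, reworded |
| Arrhythmia | A and B | A | Manual |

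The differences run in both directions. Arrhythmia is the only one of the four where the manual is plainly stricter.

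**Step 5: size.** The documents give no prevalence and no screening count, so the number in the gap cannot be computed. The allocation ratio is not stated either. If it is equal (an assumption), two thirds of the target, 132 × 2/3 = 88 participants, receive a stimulator, and so would about 2 in 3 of any people in the gap. That fraction multiplies an unknown that may be zero, so it yields no count.

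**The case against.** The strongest objection is that there may be no gap. Haemodynamic instability may simply describe what makes an arrhythmia potentially fatal, and then both texts cover the same people. The documents do not settle this, so the point holds only on the literal reading.

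Second, the manual is a plain-language list for users and not a restatement of eligibility. It is looser than the protocol on implanted devices and rewords the seizure rule, so it may just have dropped a clinical term. This stands as well: the manual is not a consistent standard for eligibility. It does not make the two arrhythmia rules agree.

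Third, staff review the manual with each participant before home use, and consent material is not in the public copy. The review is a genuine safeguard, though it comes after allocation. What candidates are told or asked at consent cannot be treated as missing.

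A reader might also infer more than the texts support:

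- **That the gap undermines the statement "With these precautions, electrical hazards are rare".** That sentence closes an item about electrical shock and burns. A person with this history can follow every precaution relevant to those hazards.
- **That the eligibility stimulation test breaches the precaution.** The manual is addressed to participants using the stimulator in the CCFES and cNMES groups. Nothing says it governs a test run by staff.
- **That participants were put at cardiac risk.** The Potential Risks section names no cardiac risk, and the documents show no such harm.

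**Conclusion.** The point holds as a low-severity mismatch in wording. On a literal reading, a candidate with a history of potentially fatal arrhythmia, no haemodynamic instability and no implanted device could pass eligibility, be assigned a stimulator, and only then be told not to use it.

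This rests on two assumptions: that the qualifier is a second condition and not a description, and that no consent or screening step outside this copy catches such a person. The number affected is unknown and may be zero. The design, the target of 132 and the analysis are unaffected. The case for acting is that the correction is nearly free and, if the qualifier is only descriptive, changes nothing.

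**What to change.** Use one wording in both places. By default, delete the haemodynamic qualifier from the exclusion, so that screening applies the rule the manual already states and applies it before allocation. If the study physicians confirm that the narrower rule is intended, leave the exclusion as it is and add the qualifier to the manual. That choice is clinical, and the documents give no reason for either wording.

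The cost is one line in one document. The default may exclude a few extra candidates, with no change to the target of 132.

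The Statistical Analysis Plan is written in the past tense, which suggests that enrolment has closed. In that case, use the single wording in later protocols and manuals for the device. Where the co-morbidity data listed among the baseline characteristics (Methods and Procedures) allow, report whether anyone with this history was assigned to CCFES or cNMES. That is one review of existing records, which may lack the detail to separate these arrhythmias from others.

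### The home manual's implant warning carries a supervision exception that the entry exclusion lacks and that home use makes no provision for

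*Combined protocol and SAP*

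**What the plan says.** The Exclusion Criteria bar three conditions relevant here: "cardiac pacemaker or other implanted electronic system"; "uncontrolled seizure disorder, defined as having a seizure within the previous 3months"; and "history of potentially fatal cardiac arrhythmias with hemodynamic instability". Pregnancy is also excluded.

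Under Risk Management, the protocol states that CCFES and cNMES participants receive a user's manual, which staff go through with them before they take the stimulator home. The Safety Information list sets out what the manual must contain. Four of its lines deal with medical conditions:

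- Pregnancy: "therefore, do not use the device if pregnant".
- Implants: "Electrical stimulation should not be used by patients with implanted electronic devices (cardiac demand pacemakers etc.) unless under specialized medical supervision".
- Arrhythmia: "Do not use the device if you have a history of potentially fatal cardiac arrhythmias".
- Epilepsy: "Electrical stimulation should not be used by people who have poorly controlled epilepsy".

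The same list shows how the manual words a stop-and-report instruction when it wants one. For skin reactions that do not fade it says: "If you note redness or blistering beyond this, discontinue use and inform your therapist".

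**The concern.** The manual is the written guidance a participant has between lab visits, and its content is fixed by the protocol. On implants, its rule and the entry rule differ. The entry rule is absolute; the manual allows use under specialist supervision, while home sessions are self-administered. Entry screening cannot catch a device implanted after randomization, so for that participant the manual line is the rule to hand. Someone under a cardiologist's care for a new pacemaker could think the exception describes them.

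A smaller point concerns seizures. The entry criterion gives a test that can be applied (a seizure in the last 3 months). The manual speaks only of poorly controlled epilepsy. A participant who has a first seizure during treatment, and has never been told they have epilepsy, may not see that the line applies.

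What is at stake is participant safety during home stimulation, not the validity of any comparison.

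**Working it through.** The plan states no figure on this point, so the check is mainly of wording.

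**Step 1. Compare each manual line with its exclusion.**

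| Condition | Entry exclusion | Manual line | Relation |
|---|---|---|---|
| Pregnancy | Absolute | Absolute | Same |
| Implanted device | Absolute | Barred, with a supervision exception | Manual looser |
| Arrhythmia | Potentially fatal, and with hemodynamic instability | Potentially fatal, no further condition | Manual stricter |
| Seizures | Defined by a 3-month window | Poorly controlled epilepsy, undefined | Manual vaguer |

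Of the four lines, only the implant line has an exception, and only there is the manual shown to be looser than the exclusion.

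**Step 2. Look for the supervision that the exception requires.** Methods and Procedures describes the home sessions as self-administered. At each lab session the therapist spends 15 minutes watching the home exercise, reinforcing instructions and dealing with problems. The study physiatrist appears under Risk Management, for skin irritation, burns and shocks. Neither role is described as specialist supervision of stimulation in someone with an implant.

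**Step 3. How much scheduled stimulation falls outside the lab?** Inputs are the regimens in Methods and Procedures, for a week with two lab sessions.

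- CCFES: home 10 × 2 × 22 = 440 min; lab 2 × (15 + 75) = 180 min; home share 440 / 620 = 71%.
- cNMES: home 10 × 2 × 29 = 580 min; lab 2 × 15 = 30 min (the observed home exercise only, since task practice is unstimulated); home share 580 / 610 = 95%.

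The totals of 620 and 610 min agree closely with the plan's stated aim of equal weekly stimulation in these two groups. They are session times that include the rest phases. They show that most use takes place at home; they say nothing about how often an implant or seizure occurs.

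**Step 4. Look for instructions covering a new event.** Potential Risks tells participants to notify staff of a suspected pregnancy, and to stop and make contact if stimulation is painful. The manual covers persistent redness or blistering. The supplied text has no instruction specific to a new implant or a seizure. Risk Management asks for reports of the risks listed before it. That list ends with unknown or unforeseen risks, which arguably reaches an unexpected seizure but hardly a planned implant. A request to report is also not an instruction to stop.

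**Step 5. Compare the windows for seizures.** The entry definition looks back 3 months and treatment lasts 12 weeks. Read literally, a seizure at any time on treatment would place the participant within that definition for the rest of treatment.

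**The case against.** The strongest reply is that the two texts do different jobs. Exclusion criteria decide who enters; a manual advises people already screened. Nothing requires identical wording, and nobody with an implant at screening receives the manual. This stands, and it confines the point to events that arise during treatment.

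Second, read strictly, the implant line still bars unsupervised home use, because a clinician's clearance is not supervision. This also stands. A reader might infer that the manual permits home stimulation once a cardiologist has agreed; it does not say so. The weakness is that the exception has no function in this setting and invites that misreading.

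Third, the text is an extract from the IRB protocol. Consent pages were removed, and no section on adverse events or discontinuation is shown. A reader might infer that the trial had no rule for a seizure or a new implant. The supplied text cannot support that, so the missing instruction carries little weight. The implant wording does not depend on it.

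Fourth, therapists see participants about twice a week and deal with any problems raised. This lowers the practical risk. As described, though, that time is spent on the home exercise, with diary reconciliation aimed at adherence; no question about new medical events is mentioned.

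Finally, a reader might take the seizure line to be looser than the entry criterion. The documents do not show this. Poorly controlled epilepsy is undefined, so it is vaguer and not contradictory.

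**Conclusion.** The point holds for the implant line: the protocol prescribes a manual instruction with an exception that its own exclusion does not have, for a setting in which the required supervision is not described. The seizure line merits clarification, and no more.

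The size is small. It affects only CCFES and cNMES participants with a new-onset event during the 12 weeks, and a participant would have to misread the implant line, or fail to recognize the seizure line, for stimulation to continue. It would be tempting to attach an expected number of events or harms. The documents give no rates for either event, so any such figure would be invented.

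Eligibility, the primary endpoint, the target of 132 and the analysis are unaffected. The SAP is written in the past tense, so the correction mainly serves later use of the manual. The conclusion assumes that the manual was issued with the wording listed and that no other participant document overrides it.

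**What to change.** In the manual's implant line, delete the closing clause (the five words from 'unless' on). Then add one instruction covering both events, in the form already used for persistent redness or blistering. Suggested wording: *If you receive an implanted electronic device, or have any seizure, during the study, stop using the stimulator and tell the study team.*

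State what follows in the protocol. A new implant ends stimulation outright, in line with the exclusion; leaving resumption to a clinician would restore the exception just removed. After a seizure, stimulation stays paused unless the study physiatrist clears it. That is a deliberate allowance for judgement, since applying the 3-month window literally would stop treatment for good.

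The cost is a small edit to the manual and a sentence or two in the protocol. The downside is an occasional pause in stimulation, possibly after a seizure that proves unrelated. No new staff, visits or procedures are needed.
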